#### **Safety Measures:**

Aberrant Behavior Checklist – Irritability (ABC-I): The ABC is an informant rating instrument that was empirically derived by principal component analysis to measure behavior in those with developmental disability and ASD. It contains 58 items that resolve into 5 subscales. The subscales and the respective number of items are as follows: (a) irritability – 15 items, (b) lethargy/social withdrawal – 16 items, (c) stereotypic behavior – 7 items, (d) hyperactivity/noncompliance – 16 items, and (e) inappropriate speech items. The ABC was designed to be completed by any adult who knows the patient well, such as a parent/caregiver or teacher. This instrument measures behavior on a four point severity scale where 0 = no problem at all, 1 = behavior is a problem but in a slight degree, 2 = problem is moderately serious, and 3 = problem is severe in degree. As suggested by the FDA, we have included the

ABC-I subscale as a prospective assessment for suicidal ideation and behavior at every visit. Given the concern over the possibility of increased temper tantrums raised by a previous study of high dose IN-OXT in the PWS population, the ABC-I can also inform investigators if there are any trends towards increased irritability and disruptive behavior. The Division of Psychiatry Products (DPP) has developed a policy that all clinical protocols for products developed in DPP, whatever the indication, include a prospective assessment for suicidal ideation and behavior. Per the DPP, these assessments need to be included in every clinical protocol at every planned visit and in every phase of development. Collecting this data ensures that patients in clinical trials who are experiencing suicidal ideation or behavior are detected and adequately managed. This is important whether or not a particular drug is associated with treatment-emergent suicidal behavior. As per the recommendation of the FDA, in studies of subjects with ASD, investigators frequently use the ABC-I subscale to fulfill this requirement. The ABC may help identify any increased risk to self through observation rather than self-report. In particular, the ABC-I can be useful for obtaining information about treatment-emergent irritability, self-injurious behavior or worsening of aggressive behavior. The ABC will be completed at every visit and requires approximately 25 minutes.

*Monitoring for Co-morbidities-* The study doctor will monitor hypogonadism, sleep apnea and lethargy throughout the course of the study.

*Hormone Levels*: Ghrelin, Pancreatic Polypeptide, Peptide Y, Leptin, insulin, glucagon, GLP-1, Growth Hormone, Testosterone and Estrogen will be measured using blood plasma at baseline and endpoint.

#### **COVID-19 Related Assessments:**

COVID Stressors questionnaire: This questionnaire will be used to assess any changes in eating patterns or weight changes caused due to COVID-19 stressors.

#### Adverse Event Reporting and Measures of Compliance:

Drug accountability will be completed by the Pharmacist at the Clinical Research Pharmacy and will serve as a measure of study compliance. IN-OXT and Placebo nasal spray bottles will be weighed pre-and post- dispensing to ensure the correct amount of drug/placebo was administered to the patient. The pharmacist will notify the study team if a subject is non-compliant with the study drug/placebo, and the study team will address this with the subject and his/her parent.

Adverse events will be reported on logs kept in the subject binder and completed by the study physician at each visit. Reporting requirements for the FDA (within 7 days) and the IRB (within 5 days) will be followed for any suspected unexpected related adverse event. For any SAE the IRB will be notified within 24 hours, and the FDA within 48 hours.

#### **Special Circumstances**

During special circumstances (e.g. COVID-19 pandemic), the specific guidance from local public health and other competent authorities regarding the protection of individuals' welfare must be applied. In cases where participants are not able to perform all protocol-defined assessments due to special circumstances, the investigator must discuss with the medical monitor potential mitigation approaches.

For the duration of such special circumstances, the following measures may be implemented for enrolled subjects:

**A.** Safety follow-up may be done by a telephone call, other means of virtual contact or home visit, if appropriate.

- **B.** Patient and/or clinician-rated outcomes assessments may be done by video-conference, telephone call, other means of virtual contact, if possible.
- **C.** An alternative approach for IMP dispensing, secure delivery and collection may be sought
- **D.** Visits may take place in a different location than defined in the protocol. If this is not feasible, then the visit may take place virtually with documentation of the means of communication (e.g., phone call or videoconference).
- **E.** Biological samples may be collected and analysed at a different location than defined in the protocol. Biological samples should not be collected if they cannot be processed in a timely manner or appropriately stored until shipping/processing.
- **F.** If despite best efforts it is not possible to collect the biological samples or safety assessments (e.g. ECG, vital signs), the investigator must review the benefit-risk for patient continuation in the study and record this in the medical records

The rationale (e.g., the specific limitation imposed by the special circumstances that led to the inability to perform the protocol-specified assessment) and outcome of the discussion with the medical monitor will be documented in the medical record. Information on how each visit was performed will be recorded in the eCRF.

Procedure	Time	Completed By	Scre ening (rem ote)	Baseline (in-person)	Week 2 (remote)	Week 4 (remote)	Week 6 (remot e)	Week 8 (in- person)	Week 10 Follo w Up (remo te)
Informed Consent	60 min	Parent/Child/Cli nician	x						
I/E Criteria	10 min	Clinician/ Parent	х	Х					
Medical Hx/Demographics	30 min	Parent/Child/Cli nician	x						
Hypogonadism/sleep apnea Hx	10 min	Parent/Child/Cli nician	х						
Physical/Neuro Exam	20 min	Clinician/ Child		Х				Х	
Psychiatric Interview	30 min	Parent/Child/Cli nician	х						
Intelligence Test	60 min	Clinician/ Child		Х					
Randomization	0 min			Х					
Concomitant Medications	5 min	Parent/Child/Cli nician	х	х	х	x	х	х	Х
Adverse Events/Monitoring for hypogonadism, sleep apnea, lethargy	10 min	Parent/Child/Cli nician	x	х	x	x	x	х	x
Standard Laboratory Tests*	10 min	Clinician/ Child	X***	Х				Х	
Hormone and Metabolic Laboratory Tests**	10 min	Clinician/ Child		х				х	
Treatment Given	10 min	Parent/Child/Cli nician		х		x		х	
Urine Pregnancy Test (if appropriate)	5 min	Child/Clinician	х	Х				х	
Vital signs	15 min	Clinician/ Child		Х				Х	
Eating Behavior Measures									
Hyperphagia Questionnaire- Clinical Trials (HQ-CT)	15 min	Parent/Child/Cli nician	х	х	x	x	х	x	х
Weight, Body Composition and BMI	5 min	Parent/Child/Cli nician		х				х	
Dietary Diary ASA24 Automated Self-	15 min	Parent		х				х	

Administered 24 Hour Recall									
Repetitive Behavior Measures									
Montefiore-Einstein Rigidity Scale –Revised (MERS-PWS)	15 min	Clinician		х		х		x	х
RBS-R	15 min	Parent		X [pre-dose]		х		x	х
Oxytocin Measures									
Salivary Oxytocin Levels	10 min	Clinician/Child		X [pre- and 1 hour post dose]		X [pre- and 1 hour post dose]		X [pre- and 1 hour post dose]	x
Global Clinical Improvement and Quality of Life Measures									
ABC-I (Full ABC will be completed to measure this subscale)	25 min	Parent		X [pre-dose]	х	х	х	x	х
CGI-I	5 min	Clinician			X	Х	Х	Х	Х
CGI-S	5 min	Clinician	Х	Х					
WHOQOL	20 min	Parent/Child/ Clinician		Х		х		x	х
Caregiver Strain Questionnaire	10 min	Parent		Х		Х		Х	х

\* Standard Laboratory Tests: CBC, CMP including sodium, IGF-1, thyroid panel, lipid panel, hemoglobin A1C, and urine pregnancy test
 \*\* Hormone and Metabolic Laboratory Tests: testosterone, estrogen, growth hormone, ghrelin, pancreatic polypeptide, peptide YY, leptin, GLP-1, insulin, glucagon

\*\*\* To be done at local Quest

Table 2: Intranasal Oxytocin vs. Placebo for the Treatment of Hyperphagia in Prader-Willi Syndrome SCHEDULE OF EVENTS

### RECRUITMENT

We have received letters of support from [name] from the Foundation for Prader-Willi Research, [name], [name] and [name]. We are in communication with the local chapter of the Prader-Willi Syndrome Association USA. We have also collected over 40 patients who are interested in the study and meet with inclusion/exclusion criteria. These patients contacted us after [name] presented at the Foundation for Prader-Willi Research Meeting (November 2014), Prader-Willi Syndrome Mental Health Strategy Workshop (March 2015) and the "Overcoming Bottlenecks in Clinical Trials of Investigational Medicinal Products for Hyperphagia in Prader-Willi Syndrome" FPWR Meeting (July 2015), all which were geared toward the development of clinical trials for this population. Additionally, [name] team presented at the recent Foundation for Prader-Willi Research Meeting held in Austin, Texas. These families are very enthusiastic about participating in research trials.

**[name]**, the Chair of the Scientific Advisory Board for the Foundation of Prader-Willi Research (FPWR), is a co-investigator on this proposal, brings a wealth of research and clinical PWS expertise to the proposal, and is committed to aid us in recruitment. The mission of the Foundation for Prader-Willi Research (FPWR) is to eliminate the challenges of Prader-Willi syndrome through the advancement of research. FPWR has over 1,000 members, including families in the USA, Canada and around the world with a social media reach of >7,500 individuals, and continues to grow rapidly. Their largest concentration of members is in the northeast, within quite reasonable travel distance to our institution. Their community is highly engaged and enthusiastic in its support of research; in fact, a recent online family survey indicated that more than 95% ~ 750 respondents would consider enrolling in a clinical trial. To ensure the successful completion of our clinical study, FPWR is committed to assisting us in the recruitment of participants by posting information on the FPWR website and social networks. They will also feature our study in their "Clinical Trials Alert" e-newsletter, which reaches approximately 700 families, and in their "Clinical Trials" webinar series, which is also well attended.

**Global PWS Registry:** The Global Prader-Willi Syndrome Registry is sponsored by the Foundation for Prader-Willi Research (FPWR) and hosted by the National Organization of Rare Diseases (NORD). The primary objective of the Registry is to develop a comprehensive database of individuals with PWS to better understand the full spectrum of the PWS phenotype. Secondary objectives include accelerating enrollment in clinical trials by locating potential research participants quickly and efficiently. The Registry question set was developed in collaboration with leading clinicians in the field of PWS, including Drs. [name] (University of Florida, Endocrinology); [name] (Kansas University Medical Center, Genetics); [name] (Shriner's Hospital, Orthopedic Surgery), and [name] (Cambridge University, Psychiatry). The registry will collect data from parents/caregivers (or the person with PWS, if s/he is able) with respect to Demographics (including weight, height and age), Diagnosis, Development, Medical History (eg, endocrine, neurological, orthopedic), Medications, Behavior and Appetite, Mental Health and Quality of Life.

The design and implementation of the Registry was guided by current best practices in advocacy group- sponsored rare disease registries. To this end, [name] participated in the Genetic Alliance "Registry and Biobank Boot Camp" in Washington DC (2012), while [name] attended registry-focused sessions at the annual meeting of the National Organization of Rare Disorders (2013) and at the annual DIA conference (2014), where she was a DIA Patient Advocate Fellow. Drs. [name] and [name] have also consulted with other advocacy groups who have launched successful registries and [name], Director of Patient Resources for Clinical and Translational Research, Office of Rare Disease Research, NCATS, NIH. The Registry protocol and informed consent have been reviewed and

approved by an Institutional Review Board (Chesapeake). A governing body consisting of the Registry Investigators (Drs. [name], [name], [name] and [name]), parent advocates (2), has been established.

*Predicted Enrollment:* We expect that the Foundation of Prader-Willi Research (FPWR) and their Global PWS Registry to be the greatest source of recruitment for our study. There are over **700** patients interested in participating in research that we will have access to with their Clinical Trials Alert newsletter. Additionally, the Global PWS Registry will collect data that will allow us to pre-screen patients based on our inclusion/exclusion criteria. Through [name] center we will have access to over **450** patients. [name] practice has over **300** patients with PWS. We have budgeted significant funding to provide travel reimbursement to patients that will need to travel long distances to our center and do not expect that to play an issue in the recruitment and enrollment for our study due to the enthusiasm of this population for clinical research. In total we will thus have access to, at minimum, **1450** patients and families affected by Prader-Willi Syndrome. Even if we use an elevated pre-screening/screen failure rate of 80%, to account for patients that are not interested, do not meet I/E criteria, or who do not wish to travel to our site, we would still have access to approximately **300** patients that would be study eligible.

As mentioned above, we are already in contact with 40 families/patients that are interested in research and meet the criteria for this study. Study subjects will be drawn from the resources above and referrals, as well as from the diverse and large clinical practice of the PI, [name]. Additional recruitment methods include advertisements in local media, referrals from patients' personal physicians and the clinical affiliations of the PI and collaborators. Prescreening/screening procedures are detailed below. Study visits have been kept to the safest minimum to reduce caregiver burden and travel time. Reimbursement of \$150 for each inperson visit (2 visits) and \$30 for each remote visit (5 visits) will be provided, for a total of \$450 over the course of the study. This reimbursement covers compensation for time and reimbursement for travel expenses to the site. Additional funds have been allocated to provide for long-distance travel for patients outside of the tri-state area.

**Timeline:** We anticipate completing this study in 3 years, with 10 subjects enrolled in year 1, 20 subjects enrolled in year 2, and 20 subjects enrolled in year 3. A 6 month start-up period will allow for IRB approval and an update to the IND; followed by 24 months of recruitment/enrollment and a 6 month period to complete data analysis and prepare for publication. Data will be entered into the database prospectively.

#### Assessment of Safety:

The safety and tolerability of the intranasal oxytocin will be determined by clinical laboratory results, physical examination and adverse events monitoring. Adverse Event (AE) collection will begin when subjects are enrolled and randomized at the baseline visit, and will occur throughout the study, or last study visit if the patient withdraws or is discontinued from the

study. AEs will be recorded as volunteered by the patient or solicited through indirect questioning. An AE will be

	Table 3: Adverse Event Relationship to Study Drug
Possibly Related	There is "a reasonable possibility" that the event may have been caused by the product under investigation (i.e., there are facts, evidence, or arguments to suggest possible causality). Individual AE reports will be considered "related" to the use of the product if the "not related" criteria are not met.
Not Related	There is an unreasonable temporal relationship between administration of the product and the onset of the AE (i.e., the event occurred either prior to randomization, or too long after administration of the product for it to be considered product-related); The causal relationship between the product and the AE is biologically implausible (i.e., death of a passenger in an automobile accident); There is a clearly more likely alternative explanation for the AE (i.e., typical adverse reaction to a concomitant drug and/or typical disease-related event).

considered "related" or "not related" to the use of the product based on the criteria listed in **Table 3**. Assessment of the causal relationship between any Serious Adverse Event (SAE) and study drug administration will be performed by both the Investigator and the Sponsor. If at least one of the parties assesses the event as related, it will be reported expeditiously as related to the appropriate parties (i.e. FDA and IRB). The severity of each AE should be characterized and then classified into one of three clearly defined categories as follows:

Mild: The AE does not interfere in a significant manner with the subject's normal functioning level. It may be an annoyance.

Moderate: The AE produces some impairment of functioning, but is not hazardous to health. It is uncomfortable or an embarrassment.

Severe: The AE produces significant impairment of functioning or incapacitation and is a definite hazard to the subject's health.

These 3 categories are based on the Site Investigator's clinical judgment, which in turn depends on consideration of various factors such as the subject's reports, the physician's observations and the physician's prior experience. The severity of the AE should be recorded in the source documentation. The evaluation of severity is distinguished from the evaluation of "seriousness." A severe event might not meet the criteria for seriousness and a serious event might be evaluated as mild.

**Safety Analyses:** Safety will be evaluated from concomitant medications, study drug exposure, treatment emergent adverse events, serious adverse events, death, suicidal ideation, physical examinations, clinical laboratory test results and vital signs. All summaries of adverse events and suicidal evaluation will be presented. Serious adverse events, deaths (if any), abnormal laboratory results and abnormal vital signs will be listed in patient listings. All AEs will be coded by the system organ class (SOC) and preferred term (PT) using the Medical Dictionary for Regulatory Activities (MedDRA).

Non-treatment emergent AEs are defined as

- AEs that started and resolved prior to the first study drug dosing
- AEs that started prior to the first study drug dosing, resolved after first study drug dosing and the grade remained the same or reduced.

Treatment emergent adverse events (TEAEs) are defined as all AEs that begin or worsen after the patient receives the first dose of the study drug until follow –up. All reported AEs (including non-treatment-emergent adverse events) will be listed. Overall summary of TEAEs, such as total number of reported TEAEs, total number of patients reporting at least one TEAE, severity of TEAEs, relation to study drug, serious AEs, any deaths, TEAEs leading to study drug discontinuation, will be summarized by treatment group. In addition, TEAEs will be tabulated by SOC and PT. A table will contain the number of TEAEs (frequency of occurrence, number and percentage of patients) by treatment group will be created.

For summaries of TEAEs by maximum severity, body system, and preferred term, the rule will be as follows: if a patient experiences more than one episode of a particular coded adverse event, the patient will be counted only once by the maximum severity of these episodes (preferred term). Similarly, if a patient has more than one adverse event within a body system, the patient will be counted only once by the maximum severity among adverse events in that body system. For the purpose of summary of adverse events, missing severity events will be included in the Grade 3 (Severe) event category. Summary of TEAEs by SOC and PT will also be presented fort the following categories, when data are available.

- 1. Grade 3 TEAEs
- 2. Related and Grade 3 TEAEs
- 3. TEAES leading to study drug discontinuation
- 4. Serious events
- 5. Serious and related events
- 6. Events resulting in death

Additional Safety Monitoring and Adverse Event Reporting Adverse events that are serious and unexpected will be immediately reported to the IRB, and FDA. Non-serious unanticipated problems will be described in annual reports to the IRB and FDA. Additionally, a pediatrician not affiliated with this study will serve as a medical safety monitor for this study. The safety monitor will review subjects' laboratory values and adverse events on at least a monthly basis. This physician will be available to immediately address the clinical circumstances for any acute problem and will promptly notify appropriate regulatory bodies.

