**Titration Plan and Schedule:** If side effects occur, the medical monitor, PI and co-I's will determine if and when to titrate based on severity of the adverse event and relation to the study drug. If there is a significant exacerbation of known PWS co-morbidities, including Type 2 diabetes, sleep apnea or hypogonadism, or any other adverse event rated by the study physician as severe, a clinical determination will be made by the medical monitor, PI and co-I's, as to the patient's eligibility to continue in the study, or to follow the titration schedule, as described below. Both co-investigators, [name] and [name], have extensive expertise in co-morbidities associated with PWS, as does consultant [name].

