#### Titration Schedule:

Adverse events: Study physician will review with study participants regarding the nature,

duration and severity of noted adverse events. The study physician will make clinical judgements on the relationship between reported adverse events with study medication. If there is a high likelihood of adverse events being related drug effects, the subject will titrate down from 16 IU/day (4 sprays per day) to 12 IU/day (3 sprays per day) and will be reassessed in one week). At the next assessment the side effects and tolerability will again be reviewed by the PI and medical monitor. If the side effects have resolved, the subject will be titrated back up to 16 IU/day. If the side effects persist, the subject may continue on the 12 IU/day for another week; or will be discontinued from the study at the judgement of the PI. Subjects who do not receive the full dose by week four will be discontinued. Any subject who is discontinued from the study will be referred for continued medical follow up.

Lack of response: One upward titration will be allowed at week 2 to 24 IU/day (4 sprays per day) if study clinician, with consultation of the PI, determines that study subject experiences no response on hyperphagia via a categorical yes/no determination, and has no adverse events. In our current ongoing pilot study, and in [name]'s study, the initial hyperphagia response was observed at the week 1 and week 2 ratings.

**Instructions for Dosing:** Once the cap has been removed from the spray, the device should be held upright to the nostril and the actuator depressed. The patient should be in the sitting position and should be instructed to inhale gently through the nose while the actuator is being depressed. The head should be tilted back once the actuator is depressed to ensure that no fluid runs out of the nose. Parents may assist the child with dosing.

**Outcome Measures:** Project outcomes will be determined by changes in scores of parent and clinician rated measures from baseline to week 8 and comparisons of week 8 measures between active treatment and placebo groups. Assessments will be administered according to the schedule of events in **Table 2**.

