Safety monitoring will be completed at each visit in both remote and in-clinic settings. Participant will complete concomitant medication review, adverse event (AE) monitoring, ABC rating, and be monitored for hypogonadism, sleep apnea and lethargy, In addition, a complete physical and neurological exam and full panels of clinical labs (CBC, BMP, LFT, IGF-1, thyroid panel, lipid panel, HbA1C, testosterone, estrogen, growth hormone, ghrelin, pancreatic polypeptide, peptide YY, leptin, GLP-1, insulin and glucagon) will be completed at baseline and week 8 in person visits.

For participants who are able to provide salivary samples and co-operate with the collection process, the study team will attempt to obtain pre- and 1 hour post- study IP administration saliva at baseline, week4, and week 8 using the Oragene-Discover collection kit (ORG-500). The salivary samples will be used to measure patient oxytocin levels.

As required by the Division of Psychiatry Products and suggested by FDA review, we have also included the ABC-I subscale at every visit as a prospective assessment for suicidal ideation. The ABC will also be used to assess for adverse events, including increased aggression or temper tantrums. Urine pregnancy tests will be completed at every visit to ensure subject safety. If a subject becomes pregnant during the study, she will immediately be discontinued from the medication. All subjects must use abstinence or a valid method of non-estrogen based double barrier contraception to participate in the study.

While some of these secondary measures have not been studied in PWS, we believe that they

are appropriate for this population as a valid measure of treatment efficacy and focus on important target issues of PWS – including repetitive behaviors (Repetitive Behavior Scale-Revised). The WHOQOL is a validated measure used to assess quality of life and has been used in a vast array of clinical trials in varied disorders (muscular dystrophy, hypertension, tuberculosis, etc.). The Caregiver Strain questionnaire (CSQ) is a commonly used and well-validated self-report questionnaire developed to assess caregiver strain for families with a child living with an emotional or behavioral disorder. The ABC has been used to assess disruptive behaviors in other disorders such as Down Syndrome and other intellectual disabilities

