**Study Time Commitment and Reduction of Burden:** Every effort to reduce the time burden on patients and caregivers has been made. In the era of COVID-19 pandemic and travel restriction, we are implementing telemedicine for remote visits in some of the study visits to reduce patient's potential exposure and travel, while ensure adequate study monitoring are in place.

The HQ-CT, ABC, WHOQOL, CSQ, MERS-PWS and RBS-R assessments are completed with the parent and not the patient, as specified in the schedule of events. As is the case in most clinical trials, the most significant burden to the parent and child is the screening visit, which is done remotely and avoided participant's need to travel. Each parent questionnaire takes between 5 and 25 minutes to complete and child assessments are kept to a minimum, with optional breaks to maximize patient comfort. Screening lab work will be done locally at participants nearest Quest lab. This is particularly beneficial for out of state participants. Clinical lab works are collected only at in person visits at baseline and week 8 during in person clinic visits. We have eliminated the eye- tracking measures as they are not central to our hyperphagia and repetitive behavior aims and to reduce burden. This ensures minimal burden to the family and decreases the time commitment while reducing testing bias on measures. As parent rated measures are questionnaires, no repeat testing bias is expected.

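### A child who leaves the study before week 8 has no planned post-baseline labs, physical exam or vital signs, and no specified off-drug adverse-event contact

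*Combined protocol and SAP*

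**What the plan says.** The combined protocol and SAP names its safety evidence in Assessment of Safety: "The safety and tolerability of the intranasal oxytocin will be determined by clinical laboratory results, physical examination and adverse events monitoring". Safety Analyses adds vital signs and says that abnormal laboratory results and abnormal vital signs will be listed.

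Timing is set in three places.

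- Outcome Measures: the exam and the full laboratory panels "will be completed at baseline and week 8 in person visits".
- Study Time Commitment and Reduction of Burden: "Clinical lab works are collected only at in person visits at baseline and week 8". Weeks 2, 4, 6 and 10 are telemedicine visits.
- Table 2: exam, vital signs, standard labs and hormone labs have one post-baseline mark each, at week 8. The columns are screening, baseline, weeks 2, 4, 6 and 8, and week 10 follow-up.

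Several provisions take a child out before week 8.

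- Titration Schedule: "Subjects who do not receive the full dose by week four will be discontinued". It also lets the PI discontinue a child whose side effects persist after dose reduction.
- Titration Plan and Schedule: eligibility to continue is reviewed after a severe AE, or "If there is a significant exacerbation of known PWS co-morbidities, including Type 2 diabetes, sleep apnea or hypogonadism".
- Risks: the medical monitor may end participation because of an AE.

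For a child who leaves, AE collection starts at baseline "and will occur throughout the study, or last study visit if the patient withdraws or is discontinued". Safety Analyses counts treatment-emergent events up to follow-up and makes no separate rule for early leavers. Titration Schedule adds: "Any subject who is discontinued from the study will be referred for continued medical follow up".

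**The concern.** The provisions that end participation early are mostly safety provisions, so some of the children of most safety interest are the ones who never reach the only post-baseline exam, vital signs and blood draw. A child removed for worsening diabetes or hypogonadism has no planned exit HbA1C, testosterone or estrogen. The one AE reported from the blinded pilot (Preliminary Study 4) was mild polyuria/nocturia, judged possibly drug-related. Table 2's standard labs include sodium, but a child leaving early for that same event would have no planned exit sodium.

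The second part is what happens after the drug is stopped. Whether an event resolves off drug bears on causality. A completer is asked about AEs at week 10. For an early leaver the plan neither specifies such a contact nor clearly rules one out.

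**Working it through.** **1. Is an exit visit hidden elsewhere in the schedule?** Predicted Enrollment pays $150 for each of 2 in-person visits and $30 for each of 5 remote visits, and states a total of $450.

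- Visits: 2 + 5 = 7, which equals the seven columns of Table 2.
- Payment: 2 × 150 + 5 × 30 = 300 + 150 = $450, which reproduces the stated total.

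The two counts agree, and none of the seven visits is an early-termination visit.

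**2. What each child is planned to have after baseline**

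| Safety item | Completer | Child leaving before week 8 |
|---|---|---|
| AEs, concomitant medications, ABC, and checks for hypogonadism, sleep apnea and lethargy | weeks 2, 4, 6, 8, 10 | each visit attended before leaving |
| Physical/neurological exam | 1 (week 8) | 0 |
| Vital signs | 1 (week 8) | 0 |
| Standard and hormone labs | 1 (week 8) | 0 |
| Specified off-drug AE contact | 1 (week 10) | none |

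Table 2 marks treatment at week 8, so the completer's off-drug contact falls about 10 − 8 = 2 weeks after the last dose. Of the three sources named in Assessment of Safety, two (labs and exam) have no planned post-baseline value in an early leaver.

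**3. The AE wording.** Assessment of Safety ends collection at the last study visit for a child who withdraws or is discontinued. Taken literally, that is the last remote visit attended. It could also mean a closing visit, but no content or timing is defined for one. Safety Analyses runs the treatment-emergent window to follow-up without excepting early leavers, which would need a later contact. The two sections are not reconciled.

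**4. How many children.** The documents give no stopping rate; Missing data says only that loss should be low in an 8-week trial. The rates below are assumptions, applied to 50 children:

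- 2%: 0.02 × 50 = 1 child
- 10%: 0.10 × 50 = 5 children
- 20%, as a stress value: 0.20 × 50 = 10 children

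The pilot cannot narrow this range. It reports that no child has needed dose reduction so far, but dose reduction is not the same as leaving. Only 9 children had been randomized over about 3 months, so some may not have finished 8 weeks.

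**The case against.** The strongest reply is that early leavers are far from unobserved. AE review, medications, the ABC and monitoring for hypogonadism, sleep apnea and lethargy are planned at every visit, remote ones included. A child whose dose is reduced is reassessed after one week, and the medical monitor reviews side effects after each study visit. Serious events go to the IRB within 24 hours and the FDA within 48 (Adverse Event Reporting and Measures of Compliance), and nothing says this stops at exit. Discontinued children are referred for care, a safety physician is on call, and unscheduled tests remain possible. Telemedicine was a deliberate choice to spare families travel, and no child has scheduled labs between baseline and week 8.

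Much of this stands, and it rules out two stronger readings. A reader might infer that early leavers have no post-baseline safety data; the every-visit monitoring contradicts that. A reader might also infer that AE collection definitely stops at exit; the wording is too loose, and the window to follow-up points the other way.

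What remains is narrower. None of these provisions plans an exit exam, vital signs or labs. Referral is clinical care with no stated assessments, timing or return of data, and it is silent on voluntary withdrawal. Serious-event reporting does not cover the off-drug course of non-serious events. Monthly laboratory review by the safety monitor adds no blood draw.

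**Conclusion.** The gap is real but small, and closing it is a cheap improvement. Planned post-baseline sets of labs, exam and vital signs number one for a completer and zero for a child who leaves before week 8. The AE part is a request for clarification: the plan is unclear on when collection ends, and it specifies no off-drug contact for early leavers.

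The number affected is not given and is probably low: 1 to 5 of 50 under the assumed 2% to 10%. Efficacy is unaffected. The documents do not support inferring a high stopping rate or a biased safety comparison between arms.

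The point covers children who leave the study, not those who stop the drug and stay in. It is not a criticism of laboratory frequency in general. The consent pages are not in the public file, so any withdrawal procedure set out there could not be checked.

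**What to change.** 1. Add an early-termination column to Table 2 that brings forward the week-8 exam, vital signs and labs where the family agrees. If travel is not possible, use a local draw for the labs, as at screening: "Screening lab work will be done locally at participants nearest Quest lab". The screening panel already includes HbA1C, testosterone and estrogen. A local draw does not replace the exam or vital signs.
2. Reword Assessment of Safety so that every dosed child has one remote AE contact about two weeks after the last dose, matching week 10. It should record the status of any event that led to discontinuation and agree with the treatment-emergent window in Safety Analyses. Open-ended follow-up is not needed.

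Cost per early leaver, from the Table 2 times: exam 20 + vital signs 15 + standard labs 10 + hormone labs 10 = 55 minutes in person, and AE review 10 + medications 5 = 15 minutes remotely. Payment is 150 + 30 = $180, which is that child's unused week-8 and week-10 payment; for 1 to 5 children that is $180 to $900. The sample size does not change. The downside is an earlier trip for a few families, some of whom will decline.
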